8.3 Study Treatment Discontinuation, Interruption, or Dose Reduction for an Individual Subject

Study treatment discontinuation, interruption or dose reduction will be considered if the subject experience any of the following:

- i. Treatment emergent adverse event (TEAE) of grade 3 or 4 (CTCAE V5.0) severity
- ii. Any suspected statin-related adverse event related to muscle symptoms ([Appendix 5](#))
- iii. Adverse event of muscle symptoms (e.g., myalgia, pain, or weakness) or elevated creatine kinase
- iv. Laboratory value(s) indicative of drug induced liver disease (DILI)

Specific actions taken will be as follows:

- i. TEAE of Grade 3 or grade 4 (CTCAE V5.0):

- Any possibly or probably related Grade 3 TEAE
- Any Grade 4 or higher TEAE

Aldafermin and statin will be discontinued

- ii. Any suspected statin-related adverse event (other than muscle symptoms):

Subjects will be allowed a one-time rosuvastatin dose adjustment if the subject experiences a statin-related adverse event (as determined by the PI) which would compromise the subject continuing in the study. The third-party Medical Monitor will be contacted by the study site to report a possible statin-related AE requiring intervention. Information will be collected on the AE including the specific description, history, and severity based on CTCAE grading and forwarded to the Sponsor Medical Monitor or designee for approval of the rosuvastatin/placebo dose reduction. The study team should instruct the subject to refrain from administering the rosuvastatin/placebo therapy and to repeat safety laboratory examinations as indicated by the specific AE within 72 hours. If the subject is < 2 weeks from their next visit, they should not dose the rosuvastatin/placebo therapy until the next scheduled visit. If they are \geq 2 weeks from their next study visit, an unscheduled visit should be made to repeat laboratory examinations and dispense 2 bottles (10 mg and placebo). If the AE resolves, rosuvastatin may be restarted. Subjects on rosuvastatin 20 mg or 40 mg will be restarted on rosuvastatin 10 mg. If the AE reoccurs following administration of the new dose of rosuvastatin, rosuvastatin/placebo should not be restarted and second-line lipid-lowering therapy (ezetimibe) will be considered with third party unblinded Medical Monitor approval. Aldafermin dosing will not be interrupted. Rosuvastatin Dose Reduction Algorithm also presented in [Appendix 4](#).

iii. Adverse event of muscle symptoms (e.g., myalgia, pain, or weakness) or elevated creatine kinase:

A sample will be collected for assessment of CK within 48-72 hours, and CK assessment will be repeated if needed (refer to [Appendix 5](#)). At Weeks 12 and 24, the creatine kinase (CK) level will be compared to the subject's baseline level.

- If CK level is $\leq 3x$ baseline, subject will continue on aldafermin and over-encapsulated rosuvastatin.
- If CK level is $> 3x$ baseline, CK will be repeated within 48 - 72 hours and aldafermin and rosuvastatin will be held:
 - If CK is $\leq 3x$ baseline, subject can re-start on aldafermin and rosuvastatin based on the investigator's judgement.
 - If CK is $> 3x$ and $< 5x$ baseline, repeat CK levels within 48 - 72 hours while aldafermin and rosuvastatin on hold.
 - If CK is $\geq 5x$ baseline, aldafermin and rosuvastatin will be discontinued.

Upon repeat testing for subjects previously with CK $> 3x$ but $< 5x$ baseline:

- If CK is $\leq 3x$ baseline, subject can re-start on aldafermin and rosuvastatin based on the investigator's judgement.
- If CK level is $> 3x$ baseline, subject will discontinue aldafermin and rosuvastatin.

iv. Laboratory value(s) indicative of DILI:

- a) Elevation of AST or ALT $> 2x$ above subject-specific baseline value (calculated using the average of the Day -42, Day -28 and the Day 1 values) and total bilirubin $> 1.5 \times$ subject-specific baseline value, repeat testing of ALT, AST, and bilirubin must be performed within 48 - 72 hours. If there are persistent elevations (AST or ALT $> 2x$ baseline or TBL $> 1.5x$ baseline values) upon repeat testing, then close observation (testing and physical examination 2 - 3 times per week) should be implemented and discontinuation of aldafermin and rosuvastatin should be considered (see b [below](#)).
- b) A decision to discontinue or temporarily interrupt the study drug will be considered based on factors that include how much higher than baseline ALT and AST were relative to the upper limit of normal (ULN) and how much the on study ALT and AST levels have increased relative to baseline, in addition to whether there is concomitant elevation of bilirubin or INR. Aldafermin and rosuvastatin will be discontinued or temporarily interrupted as follows:
 - If baseline measurements (BLM) were $< 2x$ ULN, discontinue if ALT or AST increases to $> 5x$ BLM
 - If BLM $\geq 2x$ ULN but $< 5x$ ULN, discontinue if ALT or AST increases to $> 3x$ BLM

- If BLM \geq 5x ULN, discontinue if ALT or AST increases to $> 2x$ BLM
- Discontinue if ALT or AST increase $> 2x$ BLM AND the increase is accompanied by a concomitant increase in TBL to $> 2x$ BLM OR the INR concomitantly increases by > 0.2
- In any subjects with signs and symptoms of fatigue, nausea, vomiting, right upper quadrant pain or tenderness, fever, rash, and/or eosinophilia ($> 5\%$).

- c) If the subject lives in a remote area, laboratory testing can be performed locally and the results should be promptly communicated to the investigator site.
- d) Close observation for suspected DILI will include:
 - Repeating liver enzyme and serum bilirubin tests two or three times weekly. Frequency of repeat testing can decrease to once a week or less if abnormalities stabilize or the study drug has been discontinued and the subject is asymptomatic.
 - Obtaining or re-confirming a detailed history of symptoms and prior or concurrent diseases.
 - Obtaining or re-confirming the history of concomitant drug use (including nonprescription medications and herbal and dietary supplement preparations), alcohol use, recreational drug use, and special diets.
 - Ruling out acute viral hepatitis types A, B, C, D, and E; autoimmune or alcoholic hepatitis; NASH hypoxic/ischemic hepatopathy; and biliary tract disease.
 - Obtaining a history of exposure to environmental chemical agents

Outside of situations listed above no aldafermin /matched placebo dose reductions will be allowed. Temporary drug holidays from aldafermin dosing ≤ 5 days will be allowed on a case by case basis for subjects for safety or tolerability but must be approved by the Sponsor Medical Monitor or designee. If drug is restarted and is still not tolerated, the subject should stop the medication as multiple drug holidays will not be allowed.

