The potential therapeutic benefits of increased FGF19 pathway activity in metabolic disease and NASH is well documented in various animal models of disease. For example, aldafermin has been evaluated in various mouse animal models of NASH, and has demonstrated improvement in the histologic, biochemical, and fibrogenic biomarkers associated with NASH-related hepatic injury (Study 13-PD-NGM282-1007). Furthermore, aldafermin produced significant reduction in steatosis, inflammation, and ballooning in mouse models of NASH (Zhou 2017). Importantly, aldafermin is devoid of proliferative activity based on chronic evaluation in rodents and non-human primates that is a potential limitation of FGF19 as a therapeutic agent (Zhou 2014). Aldafermin was selected from more than 160 variants of human FGF19 that were screened to retain robust efficacy while lacking evidence of proliferative activity in db/db mice (Luo 2014, Zhou 2014, DePaoli 2019).

The safety, tolerability, pharmacokinetics (PK), and pharmacodynamics (PD) of aldafermin have been studied in a blinded, placebo-controlled, single-ascending-dose (SAD) and multiple-ascending-dose (MAD) study in normal subjects (Study 12-0101) and in subjects with T2D (Study 13-0102). Aldafermin was safe and generally well tolerated with dose-dependent mild to moderate injection-site reactions (ISRs), increases in total cholesterol and gastrointestinal (GI) symptoms (loose stools, abdominal cramping, nausea) the most common drug-related adverse events (AEs), which were observed mainly with higher doses. Dose-dependent significant reductions in serum C4 levels were also observed after administration of aldafermin in both populations supported target engagement and suppression of CYP7A1.

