8.4 Discontinuation of Subjects from Study Participation

Subjects will be informed that they are free to withdraw from the study at any time and for any reason. The Principal Investigator (PI) may remove a subject from the study if, in the PI's opinion, it is not in the best interest of the subject to continue the study. Subjects may be discontinued due to a change in compliance with an inclusion/exclusion criterion that is clinically relevant and affects subject safety, occurrence of AEs, occurrence of pregnancy, or administration of non-permitted concomitant medication that might affect subject safety or study assessments/objectives. Notification of discontinuation will be made immediately to the Sponsor Medical Monitor or designee. In case of premature discontinuation of study participation, efforts will be made to perform all final EOT and EOS visits/assessments. The date the subject is withdrawn from the study and the reason for discontinuation will be recorded on the subject's Case Report Form (CRF). All withdrawn subjects will be followed

until resolution of any AEs or until any unresolved AEs are judged by the PI to have stabilized.

9 Study Methods

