11.2 Criteria for Determining Relationship to Study Drug

The PI will make a blinded determination of the relationship of the AE to aldafermin/matched placebo, rosuvastatin/matched placebo or ezetimibe (as applicable). All determinations of relationship will be made using a four-category system (not related, possible, probable, or definite) according to the following guidelines:

- **NOT RELATED** = an AE that does not follow a reasonable temporal sequence from administration of the drug and that can be reasonably explained by other factors, including underlying disease, complications, concomitant drugs, or concurrent treatment;
- **POSSIBLE** = an AE that follows a reasonable temporal sequence from the administration of the drug (including the course after withdrawal of the drug) and that cannot be excluded as being possibly caused by the drug (e.g., existence of similar reports attributed to the drug and/or its analogues; reactions attributable to the pharmacological effect of the drug), although other factors such as underlying disease, complications, concomitant drugs, or concurrent treatment are presumable;
- **PROBABLE** = an AE that follows a reasonable temporal sequence from administration of the drug (including the course after withdrawal of the drug) and that can be excluded as being possibly caused by other factors, such as underlying disease, complications, concomitant drugs, or concurrent treatment.
- **DEFINITE** = an AE that follows a reasonable temporal sequence from administration of the drug (including the course after withdrawal of the drug), follows a known or hypothesized cause–effect relationship, and (if appropriate) satisfies the following:
 - Positive results obtained in drug sensitivity tests
 - Toxic level of the drug present in blood or other body fluids

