#### **6.2** Adverse Events

Adverse events are collected both for the screening/baseline period pre-treatment (which are referred to as pre-treatment AEs) and for the follow-up period after treatment is initiated (which are referred to as post-treatment AEs). All adverse events will be coded using the Medical Dictionary for Regulatory Activities (MedDRA, v23.0).

Treatment emergent adverse events (TEAEs) are defined as AEs that commence on or after the date (and time if available) of first study drug administration. AEs without an onset date or time will be defined as treatment emergent, except if an incomplete date (e.g., month and year) clearly indicates that the event started prior to the start of first administration of study drug or if the AE stop date indicates that the event started or stopped prior to the start of first administration of study drug.

The severity of an AE is rated by National Cancer Institute (NCI) Common Terminology Criteria for Adverse Events (CTCAE) v5. The relationship of an AE to study drug is made using a four-category system: not related, possible, probable, or definite.

The following summary of TEAEs will be provided.

- An overall summary of any TEAEs, any TEAEs leading to study treatment withdrawal, any serious TEAEs, any Aldafermin-related TEAEs, any Rosuvastatinrelated TEAEs, and death
- TEAEs by PT in descending order of incidence
- TEAEs by primary SOC and PT
- TEAEs by primary SOC, PT and severity (CTCAE grade)
- TEAEs by primary SOC, PT and relationship to Aldafermin
- TEAEs by primary SOC, PT and relationship to Rosuvastatin
- TEAEs leading to study treatment withdrawal by primary SOC and PT
- Aldafermin-related TEAEs leading to study treatment withdrawal by primary SOC and PT
- Rosuvastatin-related TEAEs leading to study treatment withdrawal by primary SOC and PT
- Serious TEAEs by primary SOC and PT

A subject will be counted only once within each preferred term and system organ class in the summary tables. The most severe occurrence of a repeat AE, as well as the most extreme relationship of the AE to the study treatment will be used for these analyses. In addition, for the rosuvastatin-related summary tables, only subjects who received rosuvastatin will be included. All SAEs and AEs leading to study drug withdrawal and death will be provided in separate listings.

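### The mandatory Grade 3 stopping rule names possibly and probably related events but leaves out definitely related ones

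*Protocol*

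**What the plan says.** Protocol Section 8.3 works in two layers.

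- **Opening clause (discretionary).** "Study treatment discontinuation, interruption or dose reduction will be considered if the subject experience any of the following". The list that follows includes any TEAE of Grade 3 or 4, with no condition on its relationship to drug.
- **Specific actions (mandatory).** For Grade 3 and 4 events there are two triggers. One is "Any possibly or probably related Grade 3 TEAE". The other is any event of Grade 4 or above, whatever its cause. The action for both is "Aldafermin and statin will be discontinued".

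Protocol Section 11.2 has the investigator, while blinded, place each AE in one of four categories and defines each one separately. *Definite* calls for a cause-effect relationship that is known or hypothesized. Where appropriate it also calls for supporting evidence, such as "Positive results obtained in drug sensitivity tests" or a toxic drug level. SAP Section 6.2 uses the same scale: "The relationship of an AE to study drug is made using a four-category system: not related, possible, probable, or definite".

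**The concern.** The mandatory Grade 3 bullet uses two words from a scale that has three drug-related levels, and the one it omits is the highest. Taken at its word, the rule is perverse: stronger evidence that the drug caused a severe event leads to a weaker required response.

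This is a subject-level safety rule, to be applied by blinded investigators at about 40 sites. A site that kept dosing after a definitely related Grade 3 event could say it had followed the protocol. A site that stopped would be acting on an intent it had to infer.

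The situation is plausible. Protocol Section 5.2.2 lists injection-site reactions and gastrointestinal symptoms, including loose stools and abdominal cramping, among the commonest drug-related events. A known effect of that kind is one an investigator could rate *definite* on cause-effect grounds, and it need not change CK or liver tests.

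**Working it through.** There is no figure to reproduce. The check is to apply the Section 8.3 rule for Grade 3 and 4 events to each category of the Section 11.2 scale.

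| Relationship (Section 11.2) | Grade 3 TEAE | Grade 4 or higher TEAE |
|---|---|---|
| Not related | action considered | both drugs stopped |
| Possible | both drugs stopped | both drugs stopped |
| Probable | both drugs stopped | both drugs stopped |
| Definite | **not named: action considered** | both drugs stopped |

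Of the three drug-related categories, the mandatory Grade 3 stop names 2 and omits 3 − 2 = 1, the strongest.

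**Is *definite* contained in the words used?** The text does not support that.

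- The Grade 4 bullet uses cumulative wording for grade. The Grade 3 bullet beside it has no equivalent for relationship.
- The Section 11.2 definitions are not nested. *Possible* presumes that other factors may be at work. *Probable* turns on excluding other causes. *Definite* turns on the cause-effect relationship and does not mention excluding other causes. An event rated *definite* is therefore not also *possible* or *probable* by definition.
- No passage defines related as possible or stronger for the purposes of Section 8.3.

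**Do other clauses require the stop?** Each was checked against a definitely related Grade 3 gastrointestinal event with normal CK and liver tests.

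- *Statin-related events, 8.3(ii).* This covers suspected statin-related events other than muscle symptoms. It permits a one-time rosuvastatin adjustment and leaves aldafermin running, so it requires no stop of aldafermin.
- *CK rule, 8.3(iii).* It stops both drugs at 5 times baseline or more on repeat testing, or if CK remains above 3 times baseline at the further repeat. It is not triggered.
- *Liver-injury rule, 8.3(iv).* The ALT, AST, bilirubin and INR thresholds are not met. One bullet names symptoms such as nausea, vomiting and right upper quadrant pain, but it sits inside the liver-injury list and does not name loose stools or cramping.
- *Drug holiday, end of 8.3.* A break of up to 5 days may be approved case by case by the sponsor's Medical Monitor, followed by restart. The drug should stop only if it is still not tolerated after restart.
- *Section 8.4.* The investigator may remove a subject, and AEs are among the grounds. This is permission, not a requirement.

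None of these produces the immediate mandatory stop that the same event would trigger if rated *possible*.

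**The case against.** The strongest reply is that nobody would read the rule this way. A protocol that stops treatment for a possible Grade 3 event, and for any Grade 4 event regardless of cause, plainly means possible as a floor. Protocol Section 11.3 points the same way, since it treats an AE as associated with the drug once there is a reasonable possibility of causation. Most investigators would stop. This makes a drafting slip the likely explanation, but the Section 11.3 sentence concerns reporting and does not govern Section 8.3.

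A second reply is that continued dosing is not unbounded. The drug-holiday clause needs Medical Monitor approval and ends in stopping if the problem recurs, and the symptom bullet in the liver-injury list has no laboratory threshold of its own. These narrow the gap without closing it: the first allows restart, and the second belongs to the work-up of suspected liver injury.

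A third reply is that the affected set is probably small. Attribution is blinded, *definite* is a demanding category, Section 5.2.2 describes the injection-site reactions as mild to moderate, and it reports no Grade 3 gastrointestinal event. That is fair. Two of three categories measures wording, not risk.

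**Conclusion.** The concern holds on the literal text. For a definitely related Grade 3 TEAE outside the CK and liver-injury rules, the protocol requires only that action be considered, while a possibly or probably related one must lead to stopping both drugs. The defect is one omitted category out of three, and it is the strongest.

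This rests on reading the bullet as written. The intended meaning was very likely possibly related or stronger, and clinical judgement would often supply it. How many subjects could be affected cannot be derived from the documents.

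The primary endpoint, power and type I error are not affected. Nor are the safety tables, because SAP Section 6.2 summarises relationship on the full four-category scale. The point should still be corrected, because an operative safety rule should not depend on every site guessing the same intent.

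**What to change.** In Protocol Section 8.3, specific action (i), replace the first bullet with *Any Grade 3 TEAE assessed as at least possibly related (possible, probable or definite)*. This matches the Section 11.2 scale and leaves the Grade 4 bullet and the attached action as they are.

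The cost is one phrase in a protocol amendment. The SAP, sample size and data collection do not change.

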8.4 Discontinuation of Subjects from Study Participation

Subjects will be informed that they are free to withdraw from the study at any time and for any reason. The Principal Investigator (PI) may remove a subject from the study if, in the PI's opinion, it is not in the best interest of the subject to continue the study. Subjects may be discontinued due to a change in compliance with an inclusion/exclusion criterion that is clinically relevant and affects subject safety, occurrence of AEs, occurrence of pregnancy, or administration of non-permitted concomitant medication that might affect subject safety or study assessments/objectives. Notification of discontinuation will be made immediately to the Sponsor Medical Monitor or designee. In case of premature discontinuation of study participation, efforts will be made to perform all final EOT and EOS visits/assessments. The date the subject is withdrawn from the study and the reason for discontinuation will be recorded on the subject's Case Report Form (CRF). All withdrawn subjects will be followed

until resolution of any AEs or until any unresolved AEs are judged by the PI to have stabilized.

9 Study Methods

9.1 Schedule of Study Procedures

The Schedule of Study Procedures is shown in [Table 4](#). The visits should occur as close to the intended dates as possible. However, Weeks 2 and 4 will have a visit window of ± 3 days. Weeks 8, 12, 18, and 24 will have a visit window of ± 7 days. Week 25 will have a visit window of $+3$ days, and Week 30 will have a visit window of ± 7 days. Subjects attending any visits out of windows from Day 1 to Week 24/Early Withdrawal (EOT) visit should be brought back into compliance with the overall study-visit schedule as soon as possible thereafter. Subjects will return to the clinic at Week 25 and Week 30 (1 and 6 weeks after last dose) for a post-treatment response and EOS follow-up visits, respectively.

Subjects who have an LDL-C value of > 100 mg/dL and > 15 mg/dL above their Day 1 value at Week 25 will need to be re-assessed at Week 30. Subjects who have an LDL-C value of > 100 mg/dL and > 15 mg/dL above their Day 1 value at Week 30 will have an additional 4- week follow up visit to confirm their LDL-C value is ≤ 100 mg/dL or ≤ 15 mg/dL above their Day 1 value. Subjects will continue to be followed until their LDL-C value is ≤ 100 mg/dL or ≤ 15 mg/dL above their Day 1 value. Subjects whose LDL-C values are not adequately managed by their maximum tolerated rosuvastatin dose plus ezetimibe will be discontinued from study and an early withdrawal study visit will be completed. The follow up/EOS visit should be scheduled for 6 weeks after the early withdrawal study visit.

Table 4. Schedule of Study Procedures

Study Procedure	(Screening) ^b	D -42	D -28 to -1	D1	W2	W4	W8	W12	W18	W 24/EW (EOT)	W25 (Post-Tx)	W30 (EOS)
Visit Window (Days) ^a					± 3	± 3	± 7	± 7	± 7	± 7	+3	± 7
Informed consent		X										
Demographics		X										
Medical history		X										
Smoking History		X										
Inclusion/exclusion criteria		X		X								
Height		X										
Body weight, BMI, waist circumference		X		X				X		X		X
		■		■	■	■	■	■	■	■	■	■
Alcohol Consumption ^c		X										
12-lead ECG		X		X				X		X		X
Vital signs		X		X	X	X	X	X	X	X		X
Central read of locally performed historical biopsy slides, if available		X										
MRI-PDFF ^d				X				X		X		X
Liver biopsy ^e				X						X		
				■								
Prior and concomitant medications		X	X	X	X	X	X	X	X	X	X	X
Adverse events ^f		X	X	X	X	X	X	X	X	X	X	X
LISSA evaluations				X	X	X	X	X	X	X		
Chemistry (fasted \geq 10 hrs)		X ^h	X ^h	X ^{g,h}	X ^g	X ^g	X ^g	X ^{g,h}	X ^g	X ^{g,h}	X ^g	X ^g
Complete blood count		X		X	X	X	X	X	X			X
HbA1c		X		X				X		X		X
Insulin level and HOMA-IR		X		X				X		X		X
				■				■		■		■
International Normalized Ratio		X		X	X	X	X	X	X	X	X	X
Alpha fetoprotein		X										
Pregnancy test ¹		X		X	X		X		X			X
Hepatitis and HIV screen		X										
Urinalysis		X		X				X		X		X
Urine drug screen ^j		X		X				X		X		

PEth alcohol screen	X									
Fasting lipid panel	X		X ^g							
Lipoprotein particles [REDACTED]			X	X	X	X	X	X		X
Lipase			X	X	X	X	X	X	X	X
C4 and serum bile acids ^k			X ^k	X	X	X	X	X ^k	X	X
[REDACTED] [REDACTED]			[REDACTED]							
Anti-drug antibodies & NAb			X	X	X	X	X	X	X	X
ELF Panel/ PRO-C3			X				X	X	X	X
[REDACTED] [REDACTED]			[REDACTED]							
Genetic biomarker sample, including PNPLA3 ⁿ			X							
aldafermin /matched placebo in-clinic self-administration ^o			X	X	X	X	X	X		
Dispense aldafermin /matched placebo			X	X	X	X	X	X		
Dispense rosuvastatin ^p				X	X	X	X	X		
Medication compliance				X	X	X	X	X		X ^q
Lipid-Lowering Therapy Assessment				X	X	X	X	X	X ^q	X ^r

BMI = body mass index; C4 = 7-alpha-hydroxy-4-cholesten-3-one; D = Day; ECG = electrocardiogram; ELF = enhanced liver fibrosis; EOS = End of Study; EOT = End of Treatment; EW = Early Withdrawal; HIV = human immunodeficiency virus; HOMA-IR = homeostasis model assessment–estimated insulin resistance; hr. = hour; [REDACTED] [REDACTED]; LISSA = local injection-site symptom assessment; MRI = magnetic resonance imaging; PEth = phosphatidylethanol, PRO-C3 = N-terminal Type III collagen; PK = pharmacokinetic; [REDACTED]; Tx = treatment; W = week

^a Weeks 2 and 4 will have a visit window of ± 3 days. Weeks 8, 12, 18, and 24 will have a visit window of ± 7 days. Week 25 will have a visit window of $+3$ days. Week 30 will have a visit window of ± 7 days.

^b There must be a minimum of 14 days (2 weeks) between Day -42 and Day -28 Screening Visits to allow for adequate separation of baseline liver function tests. If baseline liver function tests are repeated to verify eligibility criteria have been met, there must be a minimum of 14 days (2 weeks) between the Day -28 visit and the repeat liver function tests, and Screening Day -28 to -1 will be extended an additional 14 days (2 weeks). Subjects who have completed all Screening assessments, including liver biopsy, and are eligible to participate in the study may have their Screening window extended with Sponsor approval for up to 2 additional weeks if the delay is due to scheduling conflicts.

^c During screening, sites will complete; i) AUDIT-C alcohol consumption questionnaire and, ii) document subject- reported alcohol consumption to confirm whether amounts are within protocol defined limits (refer to exclusion criterion #19)

^d Screening Day -28 MRI-PDFF (includes [REDACTED]) will serve as baseline for efficacy endpoint analysis. The Screening MRI result is valid for up to 8 weeks and may be used for a subject who is re-screened within that time frame. [REDACTED]

^e All subjects are required to have a liver biopsy result at Screening and additional liver biopsy at Week 24. A Screening liver biopsy will be performed only in subjects who do not have a historical biopsy available within 6 months of Screening.

^f Adverse events will be monitored and recorded from subject signing informed consent through follow-up.

^g Serum chemistry will include ALT, AST, ALP, bicarbonate, bilirubin (direct and total), BUN, calcium, chloride, creatinine, CK, GGT, glucose, HDL, LDL, lipase, phosphate, potassium, proteins (albumin, total protein), sodium, total cholesterol, and TG. Lab results for ALT, AST, total cholesterol, LDL, HDL, and triglycerides are blinded to the site and sponsor from Week 2 onward.

^h Creatine Kinase will be collected at Day -42, Day 1 and Week 12, and Week 24.

ⁱ A serum pregnancy test will be performed on all female subjects of childbearing potential at Day -42, -28 Screening visits and Day 1 (pre-dose). A urine pregnancy test will be performed on all female subjects of childbearing potential at Weeks 4, 12, 24, and 30. If the urine pregnancy test is positive, a serum pregnancy test will be performed to confirm

results.

^j Urine drug and alcohol screens may be repeated during treatment for subjects suspected of excessive alcohol intake or to rule out association with a safety event

^k C4 and bile acid testing will be collected at Day 1 and Weeks 2, 4, 8, 12, 18, 24, 25 and 30. In addition, for subjects participating in the optional PK sub-study, additional C4 will be tested at the same timepoints as the PK blood sample collections: Day 1 and Week 24 at pre-dose, and post-dose at 0.5, 1, 2, 4, 6, 8, 12, and 24 hours.

^l PK blood samples will be collected in all subjects before dosing themselves in the clinic (pre-dose) on Day 1, and Weeks 2, 4, 8, 12, 18, 24, and 25. On Day 1, and Week 24, a 2-hour post-dose sample will be collected. Week 24 PK testing should be done at the 2-hour post time point after the subject has injected their last dose of aldafermin /matched placebo.

^m For subjects participating in the optional PK sub-study, blood samples will be collected when the subjects dose themselves in the clinic on Day 1, and Week 24 at pre-dose, and post-dose at 0.5, 1, 2, 4, 6, 8, 12, and 24 hours. The window for sample collection for the pre-dose through 8-hour time points is ± 5 minutes. The window for sample collection for the 12- through 24-hour time points is ± 30 minutes

ⁿ A blood sample for genetic biomarker testing will be collected predose on Day 1

^o Subjects will be instructed to self-inject aldafermin daily at the same time each day in the abdomen. Subjects will not self-inject aldafermin at home on clinic visit.

^p Rosuvastatin will be dispensed at Weeks 2, 4, 8, 12, and 18 visits and subjects will be provided further dosing instruction based on their LDL-C levels and whether they are statin-naïve versus statin experienced. Subjects on a statin at screening will switch from their current statin to 5 mg (Asian subjects) or 10 mg (non-Asian subjects) rosuvastatin at Week 2 and will be dispensed additional rosuvastatin at Week 24 and continue through Week 30.

^q Medication compliance will be assessed at Week 30 only in subjects who were statin experienced at Baseline.

^r Subjects who have an LDL-C value of > 100 mg/dL and > 15 mg/dL above their Day 1 value at Week 25 will need to be re-assessed at Week 30. Subjects who have an LDL-C value of > 100 mg/dL and > 15 mg/dL above their Day 1 value at Week 30 will have a 4-week follow-up visit to confirm their LDL-C value is ≤ 100 mg/dL or ≤ 15 mg/dL above their Day 1 value.

